Cost effectiveness is an important issue and while combination of IVIG and rituximab has been advocated, the cost of such treatment is substantial and whether it poses any benefit over rituximab alone, or with other more conventional immunosuppressive agents, has not been established. Both treatment approaches have been previously published in high impact journals.^{3,5} In this study, we aim to evaluate the efficacy and safety of early use of rituximab with or without IVIG in patients with moderate to severe pemphigus using protocols that were similar to those previously published. Apart from complete remission and adverse effects, we will also aim to measure the impact of health care economics and in doing so, assess the cost and benefits of both treatment arms.

Hypothesis:

IVIg in combination with Rituximab is more superior than Rituximab alone in the treatment of moderate to severe pemphigus.

Methods:

Prospective multi-centre, randomised open-label trial

Patients will be randomised to two treatment arms: Rituximab alone or Rituximab + IVIG

Aim to recruit ~10 patients per arm (20 patients in total)

Patients will be reviewed monthly for the first 6 months then 3 monthly in clinic thereafter, follow up will be up to 4 years.

When patient enrolment is confirmed and written consent is obtained, the investigator will open the envelop sequentially and patient will receive the treatment plan stated on the allocation slip. Patient will be randomised to either rituximab arm or rituximab and IVIG arm. The random allocation sequence will be generated using computer-generated random numbers. Randomisation will be to the two arms of the trial in 1:1 ratio. The allocation sequence will be printed on paper slip. A non-study related research assistant will put the slips in to sequentially numbered, opaque, sealed envelopes.

Arm 1 (Rituximab alone arm):

- Rituximab infusion 375mg/m² body surface area (BSA) weekly for 4 weeks from baseline
- Rituximab infusion 375mg/m² BSA weekly for 4 weeks at week 24
- Rituximab infusion 375mg/m² BSA weekly for 4 weeks at week 52
- A total of 12 doses of rituximab will be given in 55 weeks
- If a patient relapses after initial rituximab infusion, further rituximab infusion 375mg/m² BSA weekly for 4 weeks can be given at time of relapse/or if patient fails to achieve complete remission 2 months from last dose of rituximab.

Week 0, 1, 2, 3	Rituximab (375mg/m ²)
Week 24, 25, 26, 27	Rituximab (375mg/m ²)

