Current practice/treatment in local hospital (IVIG +Rituximab) and existing side effects

IVIG and rituximab combination therapy has not been used in local hospitals for the treatment of pemphigus. This is a pilot study in Hong Kong comparing the use of combination therapy with IVIG and Rituximab versus rituximab alone in the treatment of pemphigus. Ahmad *et al.*⁸ found that combination therapy with IVIG and rituximab in 10 patients with pemphigus with contraindications to systemic corticosteroid resulted in long-term sustained remission (> 6 years). Of note there were lack of adverse events, no infections, deaths or hospitalisations.

Criteria:

Ages Eligible for study : 18 years to 70 years (Adult, Older Adult), by the day of signing informed consent

Sexes Eligible for study : All

Inclusion Criteria:

- Written informed consent obtained from patient
- Ages Eligible for Study: 18 years to 70 years (Adult, Older Adult)
- Newly or recently diagnosed (less than 18 months) diagnosed pemphigus vulgaris or pemphigus foliaceus based on clinical features; histological features of acantholysis via skin or mucosal biopsy; and intercellular staining pattern of indirect immunofluorescence or serological detection of DSG 1 or DSG 3 by enzyme-linked immunosorbent assay (ELISA)
- Moderate to severe active disease, as defined by overall PDAI \geq 15 or skin involvement BSA \geq 5%.⁹ [Annex 1]
- Receiving standard-of-care oral prednisolone up to 1.5 mg/kg/day
- Women who are sexually active and not postmenopausal, agreement to remain abstinent or use 2 effective methods of contraception.
- Ability to comply with study protocol as deemed by investigator's assessment

Exclusion criteria:

- Age <18 or >70
- Pregnant women or nursing mother
- Already diagnosed pemphigus patients diagnosed > 18 months
- Non-consenting patients, or patient who cannot be followed up regularly
- Patient with history of serious allergy or anaphylactic reaction to monoclonal antibody treatment
- Severe heart failure (NYHA Class III or IV)
- Unstable angina or myocardial infarction within last 3 months or post-infarction heart failure
- Anaemia (haemoglobin $<10\text{g/dL}$), Neutropenia ($<1000/\text{mm}^3$), Lymphopenia ($<900/\text{mm}^3$), thrombocytopenia ($<100,000/\text{mm}^3$)
- Renal insufficiency eGFR <60
- Liver insufficiency of ALT/AST > 2 times normal limit range
- Positive test results for hepatitis C (HCV) serology at screening
- Blood test positive for HIV

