Viral hepatitis is a major healthcare burden especially in Hong Kong, which is considered to be part of an endemic region. The seroprevalence of anti-HepBc is estimated to be as high as 37.3%,¹¹ therefore the exclusion of HepBs Ag positive and HepBc Ab positive patients were amended in study protocol, and these patients will be included in the study.

Baseline HepB DNA levels will be done for patients who are HepBs Ag positive, and anti-hepBc Ab positive

Patients will be monitored for AST and ALT levels at least every 3 months, HepBsAg and HBV DNA tests repeated whenever clinically indicated

Patients who are HepBs Ag positive – will be started on entecavir 0.5mg daily, and will be referred to a gastroenterologist for further follow up.

Patients who are HepBs Ag negative, and HBc Ab positive, with detectable HepB DNA levels – will be started on entecavir 0.5mg daily, and will be referred to a gastroenterologist for further follow up.

Patients who are HepBs Ag negative, HBc Ab positive, with no detectable HepB DNA levels, will be started on entecavir 0.5mg daily, and will be continued on entecavir for at least 18 months after completion of last dose of rituximab.^{12,13}

Monitoring and definitions of disease outcome parameters:¹⁴

- **Control of disease activity:** Time at which new lesions cease to form and established lesions begin to heal.
- **End of consolidation phase:** Time at which no new lesions have developed for a minimum of 2 weeks and approximately 80% of lesions have healed
- **Complete remission:** The absence of new or established lesions
- **Complete remission off therapy:** The absence of new or established lesions while the patient is off all systemic therapy for at least two months.
- **Relapse/flare:** Appearance of ≥ 3 new lesions/month that do not heal spontaneously within 1 week, or by the extension of established lesions, in a patient who has achieved disease control

Steroid regimen and tapering:

Prednisolone tapering³

Severe Pemphigus (PDAI ≥ 45):⁹

- Prednisolone 1mg/kg/day for 1 month, then 0.75mg/kg/day for 1 month then 0.5mg/kg/day for 1 month, then 0.3mg/kg/day for 1 month then 0.2mg/kg/day for 1 month, then 0.1mg/kg/day for 1 month then off

Moderate pemphigus (PDAI ≥ 15):⁹

- Prednisolone 0.5mg/kg/day for 1 month, then 0.3mg/kg/day for 1 month then 0.2mg/kg/day for 1 month then off

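### Severity balance is left to chance: one 1:1 allocation sequence for 20 patients names no severity stratum and does not say whether the list is restricted

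*Protocol*

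**What the plan says.** The Methods section of the Protocol calls the study a "Prospective multi-centre, randomised open-label trial" and sets its size as "Aim to recruit ~10 patients per arm (20 patients in total". On allocation it says "The random allocation sequence will be generated using computer-generated random numbers" and "Randomisation will be to the two arms of the trial in 1:1 ratio". On concealment it says "A non-study related research assistant will put the slips in to sequentially numbered, opaque, sealed envelopes"; the investigator opens these in order after consent. The text refers to one sequence and one series of envelopes. It names no stratification factor, blocking or minimisation, and it does not say that the list is unrestricted.

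The inclusion criteria admit a wide range of disease: "Moderate to severe active disease, as defined by overall PDAI" of at least 15, or skin involvement of at least 5% of body surface. The section on steroid regimen and tapering then divides patients by PDAI. One group is headed "Severe Pemphigus (PDAI ≥ 45" and has a six-month taper that begins "Prednisolone 1mg/kg/day for 1 month, then 0.75mg/kg/day for 1 month then 0.5mg/kg/day for 1 month". The other is moderate disease, with a three-month taper.

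The primary outcome is the percentage of patients in relapse-free complete remission. The Outcome measures section plans tests of baseline homogeneity and a log-rank test for relapses or flares. It mentions no adjustment for severity.

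**The concern.** The protocol treats PDAI 45 as the line between two levels of background steroid, yet the allocation it describes does nothing to spread patients above and below that line evenly over the arms. With about 10 patients per arm, one patient is 10 percentage points of the primary outcome. An uneven split of severe patients therefore carries differences in both disease burden and scheduled steroid into the remission comparison.

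The planned baseline tests cannot cure this. A test can at most detect imbalance, and with about 10 per arm it has little power to do so. Nor can stratified allocation wait for a later document, because strata must be fixed before the first envelope is filled.

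**Working it through.** **Inputs from the Protocol.** Total 20, ratio 1:1, about 10 per arm (Methods); two tapers split at PDAI 45 (Steroid regimen and tapering). The protocol gives no power calculation, no expected share of severe patients and no remission rates by severity. The only planned figure to reproduce is 20 × 1/2 = 10 expected per arm, which agrees with the target.

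**1. Scheduled steroid.**
- Severe: 1 + 0.75 + 0.5 + 0.3 + 0.2 + 0.1 = 2.85 mg/kg/day × months.
- Moderate: 0.5 + 0.3 + 0.2 = 1.00.
- The ratio is 2.85. With 30-day months the totals are 85.5 and 30 mg/kg.
- A gap of 30 points in the share of severe patients shifts mean scheduled exposure between arms by 0.3 × 1.85 × 30 = 16.7 mg/kg; a gap of 40 points shifts it by 22.2 mg/kg.

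**2. Arm sizes, if the list is simple randomisation.** Arm size is Binomial(20, 0.5).
- P(10:10) = 184,756 / 1,048,576 = 17.6%.
- P(13:7 or worse) = 275,960 / 1,048,576 = 26.3%, so P(8 to 12 per arm) = 73.7%.
- Efficiency relative to 10:10 is 4·n₁·n₂/20²: 96% at 8:12, 91% at 7:13, 84% at 6:14.

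**3. Severity balance with 10:10 forced and no strata.** Let S of the 20 be severe and k of them fall in one arm. Then P(k) = C(S,k)·C(20−S,10−k)/C(20,10), and the gap in severe share is |2k − S|/10. The protocol gives no S, so 6 to 14 is assumed. The results for S and 20 − S are the same.

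| Severe of 20 | P(gap ≥ 30 points) | P(gap ≥ 40 points) |
|---|---|---|
| 6 or 14 | 26,026/184,756 = 14.1% | 14.1% |
| 7 or 13 | 64,636/184,756 = 35.0% | 5.7% |
| 8 or 12 | 31,372/184,756 = 17.0% | 17.0% |
| 9 or 11 | 68,332/184,756 = 37.0% | 7.0% |
| 10 | 33,052/184,756 = 17.9% | 17.9% |

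With even S the gap can only be 0, 20, 40, … points, so 30 or more means 40 or more (7:3 or worse when S = 10). With odd S a gap of exactly 30 is possible and common. The range 14% to 18% therefore belongs to even S; odd S gives 35% to 37%. Under simple randomisation the chance of a gap of 30 points or more is 15% to 27% over all S from 6 to 14. Blocking alone does not balance severity.

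**4. Effect on the remission difference (assumed prognostic gap).** Suppose remission differs by g = 20 to 40 points between moderate and severe disease.
- A 7:3 split of 10 severe patients shifts the arm difference by (0.7 − 0.3) × g = 8 to 16 points.
- For comparison, the standard error at 50% remission with 10 per arm is √(2 × 0.25/10) = 22 points.
- If half the patients are severe and overall remission is 50%, severity accounts for 0.25·g²/0.25 = g² of the outcome variance, which is 4% to 16%. That is about what balancing and stratified analysis could remove.

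**The case against.** Three stronger readings are tempting, and the document supports none of them.

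**That the list is unblocked.** A reader might infer this from the wording. Computer-generated random numbers name the source of randomness, not the restriction; a permuted-block list or a fixed 10 + 10 list is made the same way. Keeping block details out of a protocol is also sensible where the trial is open-label and the investigator opens the envelopes. The protocol is silent on restriction, so the figures in step 2 hold only if the list is simple.

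**That the trial will miss a promised 10 per arm.** The target is approximate. The 17.6% chance of exactly 10:10 tests a promise that was not made, and the usual imbalance costs little efficiency.

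**That imbalance biases the result.** It does not. Over repeated randomisation, chance imbalance favours neither arm, and it is already part of the 22-point standard error. The shift of 8 to 16 points needs both an assumed prognostic gap and an unlucky split.

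Two further objections stand in part. The ratio of 2.85 compares scheduled totals and applies equally in both arms. Actual exposure may differ, since patients may enter on prednisolone up to 1.5 mg/kg/day, and those who qualify on body surface alone with PDAI below 15 match neither taper. And in a study that calls itself a pilot, the gain is modest.

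What the objections leave untouched is stratification. One sequence in one numbered series, with no factor named, is not a severity-stratified scheme; whether the list is blocked does not alter that. The restriction can be declared without revealing block sizes.

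**Conclusion.** The point holds as a cheap improvement to the design, not as an error that invalidates it. As described, severity balance is left to chance, and the protocol does not say whether the list is restricted.

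With equal arms and no strata, a gap of 30 points or more in the share of severe patients has a probability of 14% to 18% for even numbers of severe patients from 6 to 14, and 35% to 37% for odd numbers. This rests on that assumed range. On the further assumption of a 20 to 40 point prognostic gap, with half the patients severe and 50% remission overall, the avoidable part is about 4% to 16% of the variance of the remission comparison. It is avoidable chance error, not bias. Arm size is the lesser matter and arises only if the list is simple.

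**What to change.** Before the first envelope is filled, prepare two restricted 1:1 lists: baseline PDAI 45 or above, and below 45. Record PDAI before an envelope is opened. The score is already needed to assign the taper, and patients who enter on body surface alone with PDAI below 15 fall in the lower list. Vary the block sizes, conceal them from investigators and, because the trial is open-label, do not rely on blocks of 2. The non-study assistant fills two numbered envelope series. State in the Methods that allocation is restricted and stratified by these bands, without giving block sizes. With only 20 patients, add no further strata.

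Analyse by the same two bands: the primary remission percentage, for example by an exact stratified test, as well as the log-rank test. Stratifying the log-rank test alone would leave the primary outcome untouched.

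The cost is a second envelope set and some predictability of allocation, with no extra visits or staff. Near-equal arms can be expected, but exactly 10:10 is not guaranteed, because either list may stop within a block. The gap within a list cannot exceed half the largest block. With a largest block of 4 that is 2 per list, so at worst 12:8 overall; with a largest block of 6 it is 3 per list, so at worst 13:7.

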Week 52, 53	Rituximab (375mg/m ²)
Week 76, 77	Rituximab (375mg/m ²)

Arm 2: (Rituximab and IVIG arm):⁵

- Rituximab (375 mg/m² BSA) once a week for 4 weeks (week 1, 2, 3) and
- Week 4: Rituximab + IVIG 2g per kg
- Week 5, 6, 7: Above treatment repeated for 2nd cycle, infusion of rituximab (375 mg/m² BSA) once a week for 4 weeks (week 5, 6, 7) and
- Week 8: Rituximab + IVIG 2g/kg
- In week 12, 16, 20, 24 patients received a single infusion of rituximab (375 mg/m² BSA) plus infusion of 2g/kg IVIG
- Thus in 24 week period patients received a total of 12 infusions of rituximab and 7 infusions of IVIG
- If a patient was clinically free of disease at end of 24 weeks, additional infusions of IVIG will be given at week 30, 38, 48, 60 and 76
- A total of 12 doses of rituximab will be given and 12 cycles of IVIG will be given
- If a patient relapses or flares during the treatment, four infusions of rituximab at 375mg/m² BSA will be given at 1-weekly interval will be administered and IVIG 2g/kg will be given at week 4 of treatment after week 32

Week 0	IVIG 2g/kg, divided total dose given over 2-5 days
Week 1, 2, 3	Rituximab (375mg/m ²)
Week 4	Rituximab (375mg/m ²) + IVIG
Week 5, 6, 7,	Rituximab (375mg/m ²)
Week 8	Rituximab (375mg/m ²) + IVIG
Week 12	Rituximab (375mg/m ²) + IVIG
Week 16	Rituximab (375mg/m ²) + IVIG
Week 20	Rituximab (375mg/m ²) + IVIG
Week 24	Rituximab (375mg/m ²) + IVIG
Week 30	IVIG
Week 38	IVIG
Week 48	IVIG
Week 60	IVIG
Week 76	IVIG

For both study arms:

- After initial induction phase for both arms, the time between subsequent doses of rituximab for treatment of relapse should be at least 2 months apart.
- Patients will be followed up for 4 years starting from baseline visit

IVIG and Rituximab

Ahmed et al.⁵⁻⁷ has published data and protocol combining rituximab and IVIG. The theory behind this is that IVIG:

- Contains antibodies directed against B-cell-activating factor belonging to tumour necrosis factor family
- Exact mechanism by which Rituximab and IVIG are effective in induction of prolonged sustained clinical, serological and immuno-pathological remission in patients is not clearly understood – After destroying autoantibody-producing pathogenic B cells, the repopulating B cells do not produce autoantibodies. It is conceivable that in a microenvironment that more closely resembles normal physiology and homeostasis, IVIG could initiate the process of immune restoration.

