- Signs of active infection on CXR
- Positive interferon gamma release assay Quantiferon or T.Spot TB test: must be treated with at least 4 weeks post initiation of isoniazid or other TB therapy
- Inherited or acquired severe immunodeficiency
- History of malignancy
- Patient with active severe infection (excluding fungal infections of the nail), which has required antibiotic treatment within 2 week prior to study enrolment
- Infection requiring hospitalisation or intravenous antibiotic treatment within the last 8 weeks prior to enrolment

- Past history of osteomyelitis, or fasciitis, septic arthritis within the last one year
- Patients with drug induced pemphigus. A thorough medication history will be taken to rule out drug induced pemphigus including D-penicillamine, angiotensin-converting enzyme inhibitors, angiotensin receptor blockers and cephalosporins
- Evidence of any new or uncontrolled concomitant disease that in the investigators' judgement would preclude the patients participation
- Patients with history of allergy or adverse events to IVIG or rituximab treatment¹⁰
- Treatment with intravenous immunoglobulins, plasmaphoresis within the last 8 weeks prior to randomization
- Previous treatment with rituximab or any monoclonal antibody inducing profound lymphopenia
- Treatment with live or attenuated vaccine within the last 28 days prior to randomization

Admission and follow up:

- All infusions will be performed as in-patient procedure of prospective hospital and all patients are to be follow up monthly at out-patient of the prospective Queen Mary Hospital dermatology out-patient clinic
- Patients will be followed up monthly for the first 6 months, then followed up for every 3 months up to 4 years starting from baseline visit

Outcome measures:

Patients' serum will also be taken for desmoglein antibodies and levels will be charted and independent samples t-test will be used to compare the collected data between the two groups. Homogeneity of the treatment groups at baseline will be analyzed using the Mann–Whitney U test and Wilcoxon signed-rank test for independent and dependent variables. The Kaplan-Meier method will be used to estimate the likelihood of reaching the endpoint of relapses or flares within the drug infusing period based on the intention-to-treat population, defined as all patients who has received at least one dose of study medication. The log-rank test will be used to compare time-to-event curves between treatment groups.

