Statistical analysis of results will be done with IBM SPSS statistic program version 25. All tests of significance are two-tailed, and a P value of < 0.05 is considered to indicate statistical significance.

Primary outcome:

- 1) Percentage of participants who achieve relapse-free complete remission

Secondary Outcomes:

- 2) Time to protocol defined disease flare
- 3) Duration of complete remission, evaluated by the PDAI activity score [Baseline up to end of study]
- 4) Number of protocol defined disease flares
- 5) Time to initial complete remission, evaluated by the PDAI activity score [Baseline up to end of study]
- 6) Change in health-related quality of life as measured by the Dermatology Life Quality Index (DLQI) Score [Time Frame: Baseline, Week 4, 12, 24, 36, 48, 60, 72, 84, 96, 120, 144, 168, 192]
- 7) Occurrence of severe treatment adverse events (grade 3 or 4) based on common terminology criteria for adverse events (CTCAE), or death from any cause
- 8) Blood DSG 1 and 3 levels [Baseline week 0, week 4, 12, 20, 24, 36, 48, 60, 72, 96, 120, 144, 168, 192]
- 9) Blood lymphocyte level (CBC) [Baseline week 0, week 4, 12, 24, 36, 48, 60, 72, 96, 120, 144, 168, 192]
- 10) Blood CD19/20 mean B cell counts percentage [Time Frame: Baseline, week 4, 12, 20, 24, 36, 48, 60, 72, 96, 120, 144, 168, 180, 192]
- 11) Number of rescue therapy given

Baseline investigations prior to commencing therapy

General investigations:

- CBC
- Renal panel
- Liver panel
- Fasting Glucose/HbA1c
- Urine microscopy
- Urine pregnancy test in women of childbearing age
- Serum immunoglobulins for IgA deficiency
- B cell (CD19/20) enumeration

- DSG 1, 3 ELISA

Infective screen:

- HepBs Ag, Anti-HBs Ab, anti-HepBc total antibodies
- Anti-HCV IgG
- Anti HIV 1 and 2 (if indicated)
- CXR
- Interferon-gamma release assays

Patients who have positive IGRA test results

As Tuberculosis (TB) is endemic in Southeast Asia, should Interferon-gamma release assays result be positive, the patient will be reviewed by infectious diseases specialist and need treatment of latent TB treatment prior to starting Rituximab. Patients will need to have completed at least 4 weeks of isoniazid or treatment with other TB medications, before commencement of the study.

Patients who are HepBs Ag positive, or HepBs Ag negative and anti-HepBc Ab – positive

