Steroid sparing agents such as azathioprine or MMF are reduced to half the dose once the patient is successfully recruited into the study and will be tapered and stopped upon commencement of the study.

Relapse/ failure to achieve complete remission

- Additional infusion of weekly rituximab 375mg/m² BSA weekly x 4 will be given at the time of relapse/ or if patient fails to achieve complete remission 2 months from last dose of rituximab. After initial induction phase for both arms, the time between subsequent doses of rituximab for treatment of relapse should be at least 2 months apart.

Rituximab infusion protocol:

Pre-medications

- Paracetamol 1000mg one hour before Rituximab infusion
- IV Piriton 30 minutes before Rituximab infusion
- Methylprednisolone 100mg IV or Hydrocortisone 100mg IV half hour before Rituximab infusion

Preparation:

- IV Rituximab is prediluted at a dose of 500mg in 500ml of 0.9% normal saline (i.e. 1:1 dilution, 1 mg/ml)
- Initial infusion rate starts at a rate of 50mg/hr (50ml/hr)
- If no hypersensitivity/anaphylaxis reaction occurs, increase infusion rate in 50mg/hr (50 ml/hr) increments every 30 minutes

- Maximum infusion rate is 400 mg/hr (400 ml/hr)
- Subsequent infusion: start at rate of 100mg/hr (100 ml/hr), increase 100mg/hr (100 ml/hr) increments every 30 minutes
- Monitor temperature, BP HR, respiratory rate and SpO2 every 30 minutes

Adverse effects

Infusion-related:

- Fever, chills/rigors
- Injection site pain
- Nausea and vomiting
- Asthenia, headache, myalgia, giddiness
- Rhinitis, throat irritation
- Pruritus, rash
- Risk of infections
 - ** Infections including urinary tract infections, pneumonia, pneumocystic pneumonia, herpes simplex, herpes zoster, cytomegalovirus infection. Lung and brain abscess. Severe hypogammaglobulinaemia, and high-dose immunosuppressants may be possible risk factors for systemic infections
- Neutropenia
- Pyelonephritis
- Haemolytic anaemia
- Toxic epidermal necrolysis
- Parkinsonism

Intravenous immunoglobulins (IVIG)

Treatment dosage: 2g/kg over 2-5 days

Infusion Protocol

0 min	: 50ml/hour
15 min	: 75ml/hour
30 min	: 100ml/hour
45 min	: 125ml/hour
60 min	: 150ml/hour
75 min & beyond	: 180ml/hour

For patients receiving IVIG for first time, wait 30mins before 1st increase. Infusion rate should be less than 0.27ml/kg/hour in the following groups of patients:

- Renal insufficiency
- Diabetes mellitus
- ≥ 65 years of age
- Sepsis
- Paraproteinaemia

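### The Arm 1 bullets and the Arm 1 table place the last 2 of 12 rituximab doses 22 weeks apart (weeks 54-55 or weeks 76-77), and the protocol does not say which governs

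*Protocol*

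**What the plan says.** In the Protocol, Methods, Arm 1 (Rituximab alone arm), the bullets set out three courses of rituximab at 375 mg/m². The first runs weekly for 4 weeks from baseline, the second starts at week 24, and the third is given as "BSA weekly for 4 weeks at week 52". A further bullet sums these up: "A total of 12 doses of rituximab will be given in 55 weeks".

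The schedule table that follows the same bullets has four rows: weeks 0, 1, 2, 3; weeks 24, 25, 26, 27; weeks 52, 53; and weeks 76, 77.

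The design is described as "Prospective multi-centre, randomised open-label trial", with about 10 patients per arm. Desmoglein 1 and 3 levels (Secondary Outcomes, item 8) and "Blood CD19/20 mean B cell counts percentage" (item 10) are both measured at weeks 60, 72 and 96, among other times.

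**The concern.** The two statements of the control regimen cannot both be followed. Under the bullets, the course at week 52 has 4 doses and scheduled rituximab ends at week 55. Under the table, that course has 2 doses and a further 2-dose course follows at weeks 76-77. A patient who reaches week 54 is either due a dose or not due another for 22 weeks, and the protocol supports either answer.

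The regimen at stake is the comparator of a small randomised trial. If different patients are given different versions, neither can be called a deviation, because each matches part of the current text. The arm would then mix two exposure patterns from week 54 onwards. The serial B-cell and desmoglein results from week 60 could not be read without knowing which version each patient received.

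**Working it through.** This is a direct count of dose weeks. All inputs come from the Arm 1 bullets and the Arm 1 table. Only scheduled doses are counted; rescue doses are excluded.

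**Step 1: reproduce the plan's own figure.** Bullets: 4 + 4 + 4 = 12 doses. The third course starts at week 52 and its fourth weekly dose is at week 52 + 3 = 55. This matches the stated 12 doses in 55 weeks.

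**Step 2: count the table.** 4 + 4 + 2 + 2 = 12 doses, the last at week 77.

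**Step 3: compare dose by dose.**

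| Doses | Bullets (week) | Table (week) | Shift |
|---|---|---|---|
| 1-4 | 0, 1, 2, 3 | 0, 1, 2, 3 | 0 |
| 5-8 | 24, 25, 26, 27 | 24, 25, 26, 27 | 0 |
| 9-10 | 52, 53 | 52, 53 | 0 |
| 11 | 54 | 76 | 76 - 54 = 22 |
| 12 | 55 | 77 | 77 - 55 = 22 |

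Ten doses agree. Two of 12 (2/12 = 17%) move by 22 weeks. By week 55 the table version has delivered 10 doses, not 12.

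**Step 4: exposure at the planned samples** (Secondary Outcomes, items 8 and 10).

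| Sample | Scheduled doses so far, bullets | Scheduled doses so far, table | Weeks since last dose, bullets | Weeks since last dose, table |
|---|---|---|---|---|
| Week 60 | 12 | 10 | 60 - 55 = 5 | 60 - 53 = 7 |
| Week 72 | 12 | 10 | 72 - 55 = 17 | 72 - 53 = 19 |
| Week 96 | 12 | 12 | 96 - 55 = 41 | 96 - 77 = 19 |

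Samples up to week 48 are unaffected, because the two versions are identical through week 53.

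**Step 5: look for another explanation.**

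- *Rescue dosing.* Rescue is 4 weekly doses triggered by relapse or by failure to reach remission. It is not 2 doses at fixed weeks. Treating weeks 76-77 as rescue would also leave the table with only 10 scheduled doses.
- *A broken table.* The table crosses a page break, but every row is legible and the rows sum to exactly 12.
- *A general looseness in the tables.* Arm 2's table gives rituximab at weeks 1-8, 12, 16, 20 and 24 (8 + 4 = 12). It gives IVIG at weeks 0, 4, 8, 12, 16, 20 and 24 (7), then at 5 later weeks (7 + 5 = 12). These counts agree with the totals in the Arm 2 bullets.
- *A precedence statement.* There is none.

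**The case against.** The strongest reply is that this is a contained slip. The dose total is the same, 10 of 12 doses agree, and everything through week 53 is common to both versions. The bullets are internally consistent and carry an explicit 55-week total, so the likely correction is apparent. With about 10 patients per arm, and follow-up placed at one named dermatology clinic, drift between sites may be limited.

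Most of that stands as a limit on the size of the problem. It does not remove it. No text confirms that the bullets govern, and the table's 4 + 4 + 2 + 2 pattern also adds to 12, so it too reads as a deliberate schedule. That sites will in fact diverge is possible but not shown; the safer statement is that treating staff have no rule for choosing.

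A reader might also infer more than the documents support:

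- *That the rescue and hepatitis B rules are further contradictions.* Rescue is allowed "if patient fails to achieve complete remission 2 months from last dose of rituximab". Patients who are surface-antigen negative and core-antibody positive with undetectable DNA "will be continued on entecavir for at least 18 months after completion of last dose of rituximab". Both clocks run from each patient's actual last dose, and the 18 months is a minimum. The dates follow the dose that was given, so each rule is clear under either schedule.
- *That the relapse analysis is thereby broken.* The Kaplan-Meier analysis concerns "the likelihood of reaching the endpoint of relapses or flares within the drug infusing period". The protocol does not define that period, it would remain undefined once the Arm 1 schedule was corrected, and the definition may sit in a statistical analysis plan that is not at hand. It is a separate question.
- *That the primary outcome is biased.* Nothing in the protocol allows an effect on relapse-free complete remission to be estimated, in size or direction.

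**Conclusion.** The point holds as an inconsistency in the control-arm dosing schedule that must be corrected. Doses 11 and 12 of 12 are set at weeks 54-55 in one place and at weeks 76-77 in another, a shift of 22 weeks, with no rule for choosing. The consequence that can be shown is in scheduled exposure: 12 or 10 doses at the week 60 and 72 desmoglein and B-cell samples, and 41 or 19 weeks since the last dose at week 96.

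These figures assume scheduled doses only, given on time and without rescue. Which schedule the sponsor intended cannot be settled from the protocol, although the stated 55 weeks fits the bullets.

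**What to change.** Have the sponsor confirm one Arm 1 schedule and make the bullets and the table state it. There are two ways:

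- change the last two table rows to a single row for weeks 52, 53, 54 and 55, which agrees with the 55-week total; or
- change the third bullet to 2 doses at weeks 52-53, add a bullet for 2 doses at weeks 76-77, and change the total to 12 doses in 77 weeks.

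For any Arm 1 patient already past week 53, record which version was given.

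The cost is a wording amendment. Sample size, dose total and length of follow-up do not change. The downside is that, if both versions have already been used, some patients will become documented deviations from the schedule that is confirmed.
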